## Data Analysis

**Preliminary analyses.** Prior to analysis, all variables will be checked for out-of-range values and inter- and intra-measure consistency; frequency distributions and plots will be examined for unusual data distributions or data points. Any necessary data transformations will be employed. Initial analyses will evaluate the baseline equivalence of conditions and examine attrition effects. Baseline equivalence will consist of chi-square and grouped t-tests analyses comparing intervention condition on demographic characteristics and all baseline measures. Results of the baseline equivalency will be a test of the effectiveness of randomization. Any group differences will be treated as covariates in subsequent main-effect, moderation, and mediation analyses. Attrition analyses will consist of chi-square and grouped t-tests comparing proportion of participants in each condition who fail to complete follow-up assessments (i.e., drop-outs vs. completers); the independent variables will include intervention condition, demographic characteristics, and baseline measures. Results of main effects concerning attrition will provide information about the external validity of the study, and interaction effects will provide information about potential confounding.

**Main-effects analyses.** Tests of the general effectiveness of the Qlarity app within this three-panel (pretest, 1- month, and 3-month follow-up) randomized trial requires an analysis that accounts for the dependence of multiple assessments nested within participants that were assigned to conditions. Thus, we will test most of our research hypotheses with random effects growth models within the hierarchical and structural equation modeling (SEM) frameworks with individual variability in change in study outcomes from pretest to 3-months nested within individuals. Following Singer and Willet when constructing the longitudinal model, we will (a) examine empirical growth plots; (b) fit an unconditional means model; (c) fit an unconditional linear growth model; (d) fit unconditional non-linear models; and (e) compare models of longitudinal change from the previous two steps using the Akaike Information Criterion. Individual variability change in the outcomes from baseline to the 3-month follow-up assessment will be modeled as a function of intervention condition. Intervention condition by time interactions will test whether groups differ on individual trajectories over the course of the study period. We will also use logistic regression models reporting odds ratios (OR) to test for differential rates of abstinence at the 3-month follow-up assessments with intervention condition a two-level predictor.

**Moderator effects.** Moderating effects of demographics (gender and minority status) and number of baseline offenses will be explored by adding the moderator to the random effects growth models described above. The multiplicative interaction term between the participant level moderators constitute a three-way cross-level interaction with time in the growth models and addresses whether the level of the baseline moderator impacted the magnitude of intervention condition on change in the outcome. All significant cross-level interactions will be probed by computing sample-estimated intercepts and slopes of the trajectories of the outcomes at conditional levels of the moderator, separately, within the Qlarity and usual care group (i.e., simple trajectories) using methods described by Curran (Curran, Bauer et al. 2006).

**Mediation effects.** Growth-curve models implemented in an SEM framework will be used to explore whether observed condition effects on tobacco, alcohol, and drug use are mediated by adolescent attitudes and mindfulness. Following Preacher et al., models will be constructed by individually fitting growth models for mediators and outcomes using the growth curve model-building sequence described above to develop the best longitudinal change model. Then mediator and outcome growth curves will be combined in a single model. We will test whether (a) condition predicts change in each mediator, (b) condition predicts change in each outcome, (c) mediator change predicts outcome change, and (d) the condition effect on the outcome is significantly weaker when controlling for level or change in the mediator. Significance of indirect effects will be tested using bias-corrected bootstrapped confidence intervals.

**Process analyses.** A critical element to the program evaluation is the acceptability of the intervention to the target population, which will be assessed via rate of attrition, level of program

use, and degree of program satisfaction. Dose-response analyses will be conducted to examine the degree to which treatment engagement and retention (e.g., frequency and duration of app use, number of modules completed) predict change in the outcome measures at the post-intervention and follow-up assessments. Canonical correlation analyses will be used to examine the association between the dosage measures and outcome measures within the Qlarity condition. We will also test the hypothesis that those participants who report greater satisfaction with the intervention will have greater improvement in baseline-post scores using residual gain score analyses. Lastly, treating participant satisfaction as a process variable, we will examine the correlations between the satisfaction ratings and the amount of treatment engagement/retention.

**Missing data.** Missing data in outcome measures may result from dropout or item non-response. The mixed- growth models described above make use of maximum likelihood estimates and allow for use of all available outcome data from all assessments, reducing bias and increasing power. In general, maximum likelihood procedures, as well as imputation methods, will be used as they can provide unbiased estimates even in instances of substantial attrition. Multiple imputation procedures will follow best-practice recommendations.

**Power considerations.** The assumptions for the power estimates include a sample size of 380 participants, Type II error rate of 20% ( $\beta = .20$ ) and a 2-tailed alpha = .05. Power estimates for multilevel growth models require assumptions that are not easily established in longitudinal studies (e.g., complete data, homogeneous random-effects covariance structures within conditions). Thus we rely on the fact that power for multilevel growth models has been shown to surpass that of the mixed-model ANCOVA. The proposed growth models, then, will detect smaller differences between conditions than the ANCOVA models on which power estimates were based. Allowing for intent-to-treat analyses that makes use of all available data using missing data techniques described above and a pretest covariate  $r^2 = .25$ , there is sufficient power to detect main effects for condition of Cohen's  $d = .25$  (small effect size) and detect condition by moderator effects of  $d = .35$  (small to medium effect). The smallest subsample expected for decomposition of significant moderating effects is approximately 150 minority participants (75 per condition) which will provide sufficient power ( $>.80$ ) to detect condition effects of  $d = .40$  (medium effect). The study is also powered to detect small to medium between condition effect size differences (ORs = 2.05 – 2.25) for the logistic regression models predicting an estimated 15-20% substance use abstinence rates at follow-up. Using mediation effect size guidelines from Kenny for a model containing a dichotomous independent variable and a continuous mediator, effect sizes of .02, .15, and .40 derived from the product of  $d$  and  $r$ , represent small, medium, and large effect sizes respectively. Assuming small to moderate effects for the indirect pathway ( $r = .20$ ), the proposed sample size has sufficient power ( $>.94$ ) to detect small effect sizes or greater ( $dr = .04$ ) for tests of mediation. Process analyses involving correlation coefficients will have adequate power to detect small to medium effects ( $r = .20$ ).

**Feasibility benchmarks.** Program feasibility will be demonstrated by the achievement of the following benchmarks: (a) significant pre-post increases (e.g., Cohen's  $d > .35$ ) in emotional regulation, mindfulness, and self-efficacy, (b) significantly greater decreases in alcohol, tobacco, and other drug use for Qlarity participants; (c) a high consistent level of app usage (e.g., over 70% of users used the app at least 12 times over the 12 weeks); and (d) a high degree of youth satisfaction and ratings of app acceptability and usability (mean ratings  $> 4.0$  on the 5-point scale). Benchmarks are based on meta-analysis quantitative methods that recommend effect sizes of at least  $d >.25$  to demonstrate educationally meaningful change; a desire to show at least an average of weekly app use by a majority of participants; and a level of participant satisfaction that meets or exceeds that of Phase I.

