**Focus Groups and Usability Testing:** Twenty high-risk adolescents will be recruited to participate as test users in the development phase to give us initial reactions to mockup of modules, and a subgroup of 10 of these participants will be recruited to participate in preliminary usability testing of the modules. Feedback from usability testing will be used to inform adaptations to the app. The prototype app will then be evaluated in an efficacy trial with 380 additional high-risk adolescents. The primary outcomes of the evaluation-testing phase will be changes in adolescent substance use attitudes and behaviors and emotion regulation measured at three time points: baseline, 4 weeks post- baseline (end of treatment), and three months post-baseline. The proposed efficacy trial will evaluate the extent that the Qlarity app influences positive behavior change and will provide power estimates for later larger scale evaluation.

**Efficacy Trial:** Based on our power calculations, we will recruit 380 adolescents who are involved in the juvenile justice system. We have a long history of cooperation with the DHS and have well-established recruitment procedures. Eligible adolescents and their consenting parents will be recruited on a continual basis and will be included in the study for 3 months post-baseline. The participants will be randomly and equally assigned to the Qlarity condition ( $n = 190$ ) or the DC standard treatment condition ( $n = 190$ ) following adolescent assent and parent consent. Given that all youth will be involved in the juvenile justice system, we will assess all services offered and accessed by youth in both conditions.

Based on our prior experience, we expect many of the youth to be under orders to be participating in urine screening or other intervention services through DHS. Data from our current and prior studies with this population suggest that despite receiving random urine screens as part of their probationary status, 90% of youth are involved in ongoing alcohol, tobacco or other drug use (79% alcohol; 68% tobacco; 81% marijuana, and 53% other drug; 90% positive for one or more substance) at the time of referral. We will track additional services, including mandated urine screens, via official DHS reports and using a services utilization measure at each follow-up time point.

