## Data Collection Procedures

**Overview and timeline for the proposed data collection:** In the proposed study, a total of at least 380 youth will be recruited and baseline assessed for the study. We anticipate that approximately 10% of these will fail to complete the study, resulting in a sample of at least 342 youth with complete data and an intent-to-treat analysis strategy which will include all 380 youth. We will conduct baseline assessments and follow-up assessments at treatment completion (1 month), and at 3 month post-baseline.

**Assessments:** The *baseline assessment* primarily measures youth risk factors, as well as past and current substance use, and will consist of an in-person interview including questionnaires with the youth.

The *treatment completion (1-month), and 3-month assessments* are aimed at assessing short and longer term outcomes and will consist of two components: (a) an in-person interview and questionnaires with the youth, and (b) usability and satisfaction ratings for the Qlarity app. Because every participant has unique needs, we have standardized guidelines that allow for minor modifications to our procedures when needed. For example, staff will read aloud questionnaires for participants who are nonreaders, and computer-assisted questionnaires will be available in hardcopy format. We will travel to participant residences or other locations to conduct the interviews as needed.

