**Measures:** The following measures will be used to examine baseline demographic and pre- and post-changes in mindfulness skills, emotion regulation, and substance use: 1) Demographics, 2) Alcohol and Drug Use Survey, 3) Cigarette Use, 4) Adolescent Attitudes Questionnaire, 5) Emotion Regulation Scale, 6) Five Facet Mindfulness Questionnaire, 7) Youth Substance Use Interview (including Services Utilization), and 8) Qlarity usability and satisfaction rating. The Alcohol and Drug Use Survey is a 48-item scale that combines the Michigan Alcohol Screening Test (MAST) and the Drug Abuse Screening Test (DAST) and the Self-Efficacy for Limiting Substance Use. These scales are widely used as measures to assess the level and frequency of alcohol and drug use, use of mindfulness skills, as well as the ability to limit substance use, and have been shown to have good psychometric properties. In addition, urinary drug tests will be conducted at the baseline, 1- and 3-month follow ups. UA results will be photocopied after completion, and the UA cups will be discarded immediately; no identifying information will be recorded on the UA cups. We will use the same UA drug testing procedure that we have found to be successful in our current NIH funded study with adolescents in the juvenile justice system. All data will immediately be moved to a secure, locked location within ORI/Influents Innovations accessible only to the PI and research staff. The Services Utilization Survey is an interviewer-administered instrument that collects information about a respondent's use of a wide range of services such as in- and out-patient medical care (hospital, clinic, or office based), mental health treatment, drug and alcohol abuse treatment, and

Table 1. Measures		Assessments		
Measure	Baseline	1 Month	3 Month	
Adolescent Attitudes Questionnaire	●	●	●	
Alcohol and Drug Use Survey (MAST/DAST)	●	●	●	
Qlarity Usability and Satisfaction		●	●	
Cigarette Use	●	●	●	
Demographics	●			
Emotion Regulation Scale	●	●	●	
Five Facet Mindfulness	●	●	●	
Urine Drug Screens	●	●	●	
Youth Substance Use Interview (Services Utilization)	●	●	●	

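### Baseline balance tests decide the covariates, so baseline substance use enters the 3-month abstinence logistic model only by chance imbalance; fixing it in advance is a cheap gain in precision

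*Combined protocol and SAP*

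**What the plan says.** Under Data Analysis, Preliminary analyses, the plan runs chi-square and t-tests "comparing intervention condition on demographic characteristics and all baseline measures". It gives two uses for the results. One is diagnostic: "Results of the baseline equivalency will be a test of the effectiveness of randomization". The other sets the models: "Any group differences will be treated as covariates in subsequent main-effect, moderation, and mediation analyses". No significance level or size of difference defines a group difference, and this is the only covariate-selection rule in the documents.

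Under Main-effects analyses, "we will test most of our research hypotheses with random effects growth models", with the pretest as the first of three waves. Logistic regression is then added "to test for differential rates of abstinence at the 3-month follow-up assessments with intervention condition a two-level predictor". No other term is named for that model.

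Study Design defines abstinence by self-report over 7 and 30 days and across all substances. Table 1 shows that the Alcohol and Drug Use Survey (which includes the MAST and DAST), Cigarette Use, urine screens and the Youth Substance Use Interview are all collected at baseline.

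**The concern.** With proper randomisation, every baseline difference between the arms is a chance difference. A balance test therefore picks covariates by the accident of imbalance and says nothing about whether they predict abstinence. Baseline use, the obvious candidate predictor, would be left out of the abstinence model in most realisations of the trial although the data are in hand.

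Two things are at stake. The first is precision for the abstinence comparison. The second is a fixed analysis: a logistic OR adjusted for a prognostic covariate is conditional and lies further from 1 than the unadjusted, marginal OR, so the quantity reported would depend on which baseline tests happen to be significant.

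**Working it through.** **Inputs from the documents.** 380 youth, 190 per arm; two-sided alpha .05; power 80%; abstinence 15-20%, with the arm not stated; detectable ORs 2.05-2.25 (Power considerations). About 10% dropout, "resulting in a sample of at least 342 youth with complete data", or 171 per arm (Data Collection Procedures).

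**Assumptions.** A .05 threshold for the balance tests. Baseline use is a standard normal score x with logit P(abstinent) = a(arm) + g·x and g = √[R²/(1−R²) × π²/3]. Latent R² of .10, .25 and .40 gives g = 0.60, 1.05 and 1.48. Intercepts are set so that the marginal OR equals the plan's value.

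**Step 1: reproduce the plan's logistic power without a covariate.** Power = Φ{[|p₂−p₁|√n − 1.96√(2p̄(1−p̄))] / √[p₁(1−p₁)+p₂(1−p₂)]}.
- Overall rate 15%, OR 2.25: 10.0% v 20.0%. (0.1×√190 − 1.96×√0.255)/√0.25 = (1.378 − 0.990)/0.5 = 0.777, so power is 78.2%.
- Overall rate 20%, OR 2.05: 14.4% v 25.6%, power 78.4%.

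Read as an overall rate, 15-20% pairs with ORs 2.25 and 2.05 at close to 80% power. The stated ORs are therefore those of an unadjusted model with all 380 analysed. Read as a control rate, unadjusted power is 79.6% (15%, OR 2.05), 89.1% (15%, OR 2.25), 86.5% (20%, OR 2.05) and 93.8% (20%, OR 2.25).

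**Step 2: how often the rule selects a covariate.**
- One given measure: about 5% of trials (simulated 4.8-5.4%).
- At least one of the four use measures, assumed correlation .5: about 16%.
- At least one of the seven non-demographic baseline instruments in Table 1, one test each: 1 − 0.95⁷ = 30% if independent, 23% at correlation .5. This is a lower bound, because demographics and subscales are tested too. With an assumed 10 to 15 tests the range is about 29-54%.

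**Step 3: power for abstinence, overall-rate reading** (10,000 simulated trials per cell, Wald test; R² .10 / .25 / .40).

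| n per arm, marginal OR | Unadjusted | Test, then adjust (one measure) | Always adjusted |
|---|---|---|---|
| 190, 2.25 | 78.1 / 78.1 / 78.6% | 78.3 / 78.5 / 79.4% | 80.3 / 83.3 / 87.1% |
| 190, 2.05 | 78.9 / 78.4 / 78.3% | 78.9 / 79.0 / 79.2% | 80.8 / 84.3 / 87.9% |
| 171, 2.25 | 73.0 / 73.7 / 73.4% | 73.1 / 74.4 / 74.2% | 74.9 / 79.5 / 83.1% |
| 171, 2.05 | 74.2 / 74.0 / 74.2% | 74.4 / 74.6 / 75.1% | 76.5 / 80.6 / 84.6% |

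The plan's rule behaves almost like no adjustment. Testing four measures in place of one changes this little: at 190 per arm it gives 78.2-79.6%.

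**Step 4: control-rate reading.** Fixed adjustment gains about 1-10 points over the same R² range. The gain is smallest where power is already high: about 1-5 points at 20% and OR 2.25.

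**Step 5: validity.** Under the null at 190 per arm, rejection rates are 4.6-5.3% unadjusted, 4.5-5.2% always adjusted and 4.2-4.8% under the plan's rule. There is no inflation.

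**Step 6: a weaker covariate.** The only baseline use distribution that the documents give is overall status at referral: "90% of youth are involved in ongoing alcohol, tobacco or other drug use". A 90/10 binary covariate gains 0.1-0.9 points if its OR with abstinence is an assumed 2-3, and about 2 points at OR 5.

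**Step 7: change of scale.** Under the overall-rate reading, a marginal OR of 2.25 corresponds to a conditional OR of 2.34 / 2.52 / 2.80, and 2.05 to 2.14 / 2.31 / 2.57.

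**The case against.** The strongest reply is that little depends on this. The abstinence model is an addition; most hypotheses go to growth models in which the pretest is already a wave. The test is valid, the stated power is met without a covariate, and the size of the gain is assumed. All of that stands, and it limits the point to an inexpensive improvement.

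It can also be said that calling condition a two-level predictor describes its coding and does not exclude other terms, and that Power considerations assumes a pretest covariate with r² = .25. The first is fair: that no baseline term is planned is inferred from silence, though it is the natural reading when no other term is named. The second does not help. That r² belongs to the ANCOVA calculation for d = .25, where power is 80.3% with it and 68.3% without it. The logistic power sentence mentions no covariate.

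Baseline comparisons can also flag a failed allocation. Keeping or deleting the sentence on the effectiveness of randomisation changes no result; what matters is that test results should not choose the covariates.

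A reader might infer that the trial's main analyses lack baseline adjustment, or that the abstinence test is biased or underpowered against the plan's own claim. The documents support neither. The growth models carry the pretest, and Steps 1 and 5 show that the stated power reproduces and type I error is held. The lower figures at 171 per arm reflect dropout, not the covariate rule.

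**Conclusion.** The point holds for the 3-month abstinence logistic model only. Its covariates are left to chance imbalance, and a given baseline-use measure would enter in about 5% of trials. If 15-20% is the overall abstinence rate, the reading that fits the stated ORs, fixing a continuous baseline-use score in advance raises power at 190 per arm from about 78-80% to about 80-88%. If it is the control rate, unadjusted power is about 79-95% and the gain about 1-10 points.

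Confidence in the reading of the text is high. Confidence in the size of the gain is moderate, because it rests on an assumed latent R² of .10 to .40 that the documents neither give nor contradict. The case for fixing the covariates in advance does not depend on that size: it also settles whether the reported OR is marginal or conditional.

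**What to change.** - Replace the rule that baseline test results decide the covariates with a named, fixed set for the 3-month abstinence logistic model, used whatever the observed balance.
- Because abstinence is defined across all substances, include both the baseline MAST/DAST score (kept continuous, self-efficacy items left out) and the baseline Cigarette Use measure in the all-substance model. In any substance-specific model, use the matching measure alone.
- Do not rely on baseline abstinence status alone, which gains little. Cutting the score to four levels also costs some of the gain: at 190 per arm and OR 2.25, power is 80.0 / 81.9 / 84.8% against 80.3 / 83.3 / 87.1% with the continuous score.
- Report a standardised risk difference or marginal OR beside the adjusted OR.
- Baseline data may still be tabulated by arm descriptively.

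The cost is SAP wording; no new data or visits are needed. The small downside is that the adjusted OR is conditional and numerically larger (Step 7), which is why the marginal measure should accompany it.

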### **Stage 2: Product evaluation**

We will conduct an evaluation of the Qlarity app with 380 high-risk adolescents who are involved in the juvenile justice system. Feasibility, usability, participant satisfaction, and intervention outcomes of substance use will be evaluated in an efficacy trial. Data on: 1) frequency and duration of app use, 2) number of modules completed, 3) changes in attitudes, emotions and behaviors, and 4) type and frequency of substance use will be examined. Participants will be compensated using gift cards to Amazon in the following increments: \$20 for each of the baseline, 4 week and 3-month assessments, and \$50 bonus for completion off all three assessments. Participants in the focus groups and usability testing will receive a \$30 gift card for their time and effort.

**Study Design:** Our evaluation of the program will be conducted with 380 adolescents ages 13- 18 who are referred from the Oregon Department of Youth Services (DYS) in Lane and Multnomah Counties, Oregon. Adolescents will be randomly and equally assigned to one of two conditions: 1) Qlarity, or 2) an active comparison condition that is standard treatment through the DHS (i.e., drug court, group therapy, and case management). All participants will be instructed to attempt to reduce substance use with a target quit date of 1 month after program initiation (day 28). Self-reported 7-day and 30-day point prevalence abstinence for all substances will be measured 1 and 3 months after treatment initiation. In addition, we will collect biochemical verification of self-reported substance use; urinary drug tests will be conducted at the baseline, 1- and 3-month follow ups and will follow the same UA drug testing protocol that we have found to be successful in our current NIH funded study with adolescents in the juvenile justice system.

**Participants:** Participants will include both male and female high risk adolescents recruited from the Department of Youth Services (DYS) in Lane and Multnomah Counties, Oregon. We have a long history of successful collaborations with the DHS and have received their support for the current proposal. Inclusion criteria will be as follows: 1) ages 13-18, 2) involvement with the juvenile justice system, 3) documented substance use, 4) English-speaking, and 5) living in the community (e.g., biological/adoptive/foster parents).

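### The rule that turns baseline differences into covariates adjusts the growth-model efficacy test only if those covariates enter the slope equation, and the plan does not say that they do

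*Combined protocol and SAP*

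**What the plan says.** All of this is in the Data Analysis section unless noted.

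- **Preliminary analyses.** Chi-square and t-tests are run "comparing intervention condition on demographic characteristics and all baseline measures", so the baseline values of the outcomes are among the variables screened. The consequence of a difference is: "Any group differences will be treated as covariates in subsequent main-effect, moderation, and mediation analyses".
- **Main-effects analyses.** Most hypotheses are tested with random effects growth models in hierarchical and SEM frameworks, with "individual variability in change in study outcomes from pretest to 3-months nested within individuals". The pretest is therefore the first of three responses. The model is described as: "Individual variability change in the outcomes from baseline to the 3-month follow-up assessment will be modeled as a function of intervention condition". The test is: "Intervention condition by time interactions will test whether groups differ on individual trajectories over the course of the study period". A separate logistic regression compares abstinence at 3 months.
- **Moderator effects.** Here the plan does write out an interaction with time: the moderator terms "constitute a three-way cross-level interaction with time in the growth models". It gives no such statement for covariates added because of imbalance.
- **Power considerations.** The detectable effect of d = .25 comes from an ANCOVA with a pretest covariate at r² = .25, not from the growth model.

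The plan does not say whether an imbalance covariate enters the intercept, the slope or both. Nor does it say how an outcome's own baseline can be a covariate when it is already a response.

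**The concern.** A person-level covariate entered as a main effect explains where a participant's trajectory lies, not how steep it is. The efficacy test concerns steepness. If an analyst reads the rule as adding a main effect, the report will say that an imbalance was adjusted for while the tested estimate has not moved.

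This matters most when the imbalance is on the outcome itself. If one arm happens to start with heavier use, its mean is expected to fall back relative to the other arm without any treatment effect. That regression to the mean is part of the difference in slopes. It can add to an apparent benefit of Qlarity or hide a real one, depending on which arm starts higher.

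**Working it through.** **Inputs.** From the plan: "The assumptions for the power estimates include a sample size of 380 participants"; "Adolescents will be randomly and equally assigned to one of two conditions" (190 per arm); two-sided alpha .05; planned effect .25 SD; pretest r² = .25, so r = .5; visits at 0, 1 and 3 months; 10% dropout. Assumed: equal variances and the same correlation r between all pairs of visits (compound symmetry), with r varied from .3 to .7.

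**1. The plan's own figure.** ANCOVA needs n per arm = 2(1.96 + .8416)² × (1 − .25)/.25² = 188.4, so 189 (378 in total). With 190 per arm, SE = √(.75 × 2/190) = .0889, and power = Φ(.25/.0889 − 1.96) = .803. The stated figure reproduces.

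**2. What a main-effect covariate does to the tested estimate.** Growth models with random intercept and slope were fitted by generalized least squares with fixed variance components. Imbalances were forced on a covariate x (.25 SD) and on the outcome's baseline (about .20 SD). There were 20 simulated trials per setting.

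| Terms added | Largest change in condition × time per month, complete data | Same, 10% dropout |
|---|---|---|
| x, main effect | under 10⁻¹⁵ | .003 |
| outcome baseline, main effect | under 10⁻¹⁵ | .005 |
| x and x × time | .040 | .045 |
| outcome baseline and its × time | .027 | .027 |

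With complete data the main effect changes nothing beyond rounding. At 10% dropout the mean change from main effects was .0002 per month or less.

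**3. Size of the uncorrected shift.** The mean of times 0, 1, 3 is 4/3 and the sum of squared deviations is 4.667, so the slope weights are −.286, −.071 and .357. Given a baseline difference d0 and no treatment effect, each later difference has expectation r × d0.

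- Slope test, scaled to 3 months: 3 × [−.2857 + r(.3571 − .0714)] × d0 = −.857(1 − r)d0.
- 3-month change: −(1 − r)d0.

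At d0 = .20 SD:

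| r | Slope test | 3-month change |
|---|---|---|
| .3 | .12 SD | .14 SD |
| .5 | .086 SD | .10 SD |
| .7 | .051 SD | .06 SD |

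At r = .5 this is .086/.25 = 34% to .10/.25 = 40% of the planned effect.

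**4. Conditional false-positive rate at r = .5.** The unconditional SE of the slope difference is √(.5 × (2/190)/4.667) = .0336, so the critical value is 1.96 × .0336 = .0658. Given d0, the variance is (2/190) × [.75(.0714² + .3571²) − 2 × .25 × .0714 × .3571] = .000913, SD .0302. At d0 = .20 the mean is −.0286. The rejection probability is Φ(−1.233) + Φ(−3.124) = .110. At d0 = .25 it is .160.

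**5. How often.** The SE of d0 is √(2/190) = .1026, so the .05 threshold is .201 SD. One outcome is flagged in about 5% of trials. If 10 outcome baselines were independent (an assumption; positive correlation lowers the figure), at least one would be flagged in 1 − .95¹⁰ = 40%.

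**6. Overall error.** Over 400,000 simulated trials of the 3-month change contrast, rejection under no effect was 5.04% overall, 18.7% when the outcome's baseline was flagged and 4.3% when it was not. Baseline-adjusted ANCOVA gave 5.0% in all three.

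**7. A common baseline mean removes the shift.** With no condition difference at time 0, the estimator is t′V⁻¹d / t′V⁻¹t. Under compound symmetry with r = .5 the weights are −1/6, 0 and 1/3. Three months of slope is then d3 − .5d0, whose expectation given d0 is zero. This is also the ANCOVA contrast of step 1.

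**The case against.** The strongest reply is that the plan never restricts covariates to the intercept. In hierarchical and SEM growth models, change is itself regressed on person-level predictors, and an imbalance covariate can sit beside condition in the slope equation. Entered there, it does adjust the test. This stands: the fault is an unstated specification on which the adjustment depends. A reader might infer that the plan's remedy cannot act in the growth model; the text does not support that.

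A reader might also infer from the .11 that the trial's type I error is inflated. It is not. Randomization keeps the condition-by-time test at about 5% overall; the excess in flagged trials is offset by slightly lower rates in the rest. The direction is symmetric, so nothing here favours Qlarity systematically.

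The rule also does its job in the 3-month abstinence logistic regression, where a main-effect covariate acts directly on the condition comparison.

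Finally, modelling only the two follow-up visits would displace the three-wave growth models on which the trajectory, moderator and mediation analyses are built. Keeping those models while adding the outcome's baseline and its time interaction uses the same value as response and covariate; a check of that form was somewhat conservative (about 3% rejection under no effect). Both points limit the choice of remedy.

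**Conclusion.** The concern holds as an omission with a conditional consequence. As written, the rule does not ensure that a declared imbalance is adjusted for in the test that carries most hypotheses. Under the main-effect reading it leaves that test unchanged with complete data and nearly so at 10% dropout.

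For an imbalance of .20 SD on an outcome's own baseline, the 3-month effect is shifted by about .09 to .10 SD in either direction, and the slope test's false-positive rate is about .11. These sizes rest on r = .5, which the plan's r² implies, and on compound symmetry, which is assumed. Across r = .7 to r = .3 the shift runs from .05–.06 to .12–.14 SD. Overall type I error and the abstinence analysis are not in question.

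The change is worth making because the better method uses data already collected and is the one on which the sample size was based.

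**What to change.** 1. For every growth-model outcome, whatever the baseline tests show, make the main efficacy estimate baseline-adjusted in one of two ways: (a) keep the three-wave model, with time coded 0 at pretest, and constrain the arms to a common baseline mean; or (b) model the 1- and 3-month values with that outcome's baseline as a covariate whose effect may differ by visit. Under (b), youth with no follow-up value enter through the multiple imputation already planned.
2. State that any other covariate used for imbalance enters the growth models with its interaction with time.
3. Do not use an outcome's baseline as both response and covariate.
4. Keep the growth models for trajectories, moderation and mediation.

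The cost is a small change of SAP wording and model specification, with no new data.

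The fix also brings the analysis into line with the power basis. At r = .5 and a 3-month effect of .25, the baseline-adjusted contrast has 80% power. The unadjusted 3-month change has Φ(.25/.1026 − 1.96) = 68%. The unadjusted linear slope has Φ(.0714/.0336 − 1.96) = 57% if the full effect is present from month 1, and Φ(.0833/.0336 − 1.96) = 70% if it grows linearly.
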